A recent review and meta-analysis of these new oral anticoagulants has concluded that they were equally as good as enoxaparin but did have a higher bleeding tendency. The drugs did not differ significantly for efficacy and safety. (24)

NOACs do not require routine coagulation monitoring and seem to be the way of the future for ease of administration efficacy and tolerability. Additional research is needed to determine how these new oral anticoagulants should be used in special populations such as the obese medical or surgical patient.

[figure not shown]

Figure 1 Mechanism of Action of Anticoagulants

*Derived from Dwek et al 2012

4. Study Procedures

a. Study design, including the sequence and timing of study procedures

Patients will be recruited from our preoperative bariatric surgical clinic (Roux-en Y gastric bypass, and vertical sleeve gastrectomy). Each patient will undergo a thorough history and physical exam (routine standard of care for bariatric patients) to document demographics including: age, sex, height, weight, body mass index and absence of the exclusion criteria. See Table 1 for sequence and timing of study procedures.

Table 1. Sequence and Timing of Study Procedures

Overview of Study Visits: Specific Aims 1, 2 and 3							
Study Visit Before and After Intervention		Specific Aim 1 Specific Aim 2		Specific Aim 3			
		Pharmacokinetics (Prior to Surgery)	Pharmacokinetics (Following Surgery)	Pharmacodynamics			
1	3 to 5 Weeks Prior to Bariatric Surgery (study participant receives one 5 mg dose of apixaban)	х		х			
2	1 Month (4 to 6 weeks) Post-bariatric surgery (study participant receives one 5 mg dose of apixaban)		x	x			
3	6 Months (6 to 8 months) Post-bariatric surgery (study participant receives one 5 mg dose of apixaban)		x	х			
4	12 Months (12 to 14 months) Post-bariatric surgery * (study participant receives one 5 mg dose of apixaban)		x	х			
5	Final Exit Interview Visit (two weeks following final visit)	Review any adverse events that may have occurred throughout entire study					

Note: Research participants in each group (RYGB, n=15; VSG, n=15; Total n=30) will undergo the study protocol detailed above.

*The patient ideally will have lost at least 30% to 50% of excess body weight by 12 months

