Study population: Obese patients with a body mass index (BMI) of 35 kg/m² or greater that have been approved for bariatric surgery at the Johns Hopkins Center for Bariatric Surgery from January 2015 until all patients recruited. (See Table 3. Timeline of Study)

Consenting subjects will be hospitalized overnight in the JHBMC Clinical Research Center. A single dose of 5 mg apixaban will be administered by experienced CRU nursing staff, and blood samples for apixaban concentration and factor Xa activity will be collected before administration of the apixaban dose and at 0.5, 1, 2, 3, 4, 6, 9, 12, 18, 24, 48 and 72 hours after dosing.

The participant will be hospitalized and monitored for a 24 hour duration and then released home when they meet discharge criteria. The participant will then be asked to return back to the CRU for one blood draw at 48 hours and one blood draw at 72 hours. At hours 48 and 72 hours we will have ±4 hour window to allow for travel and check in for the participant.

The apixaban concentrations will be measured at Pfizer (all specimens will be stored and batched for shipment to a commercial laboratory), and the factor Xa activity measured at JHH under the leadership and guidance of [name] Director of the Lab. (As per [name] expertise he has recommended the *chromogenic assay* that measures factor Xa activity using reagents from Siemens.)

Dose schedule, duration, and concurrent medications:

A single dose of 5 mg of apixaban will be given at approximately one month before bariatric surgery, then 1, 6 and 12 months followingbariatric surgery. Alterations in the pharmacokinetics of the bariatric surgical patient could be due to the anatomic changes in the gastrointestinal tract, the resulting weight loss or both. By examining patients who have had undergone the surgery but have not lost adequate weight loss, we can separate the effects of these two variables. There will be no required concurrent medications. Excluded medications are strong dual inhibitors and inducers of CYP3A4 and P-glycoprotein inhibitors and inducers (see Table 2). This table has been provided by [name] who is an anticoagulant expert and co-investigator of this study.

Table 2. Excluded medications

Drug Class	Examples	Impact of co- administration	Suggested Managment	

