Before study enrollment, WOCBP must be advised of the importance of avoiding pregnancy during study participation and the potential risk factors for an unintentional pregnancy. The subject must sign an informed consent form documenting this discussion.

All WOCBP MUST have a negative pregnancy test within 24hours before receiving apixaban. The minimum sensitivity of the pregnancy test must be 25 IU/L or equivalent units of HCG. If the pregnancy test is positive, the subject must not receive apixaban and must not be enrolled in the study.

In addition, all WOCBP should be instructed to contact the investigator immediately if they suspect they might be pregnant (e.g., missed or late menstrual period) at any time during study participation.

ADVERSE EVENT REPORTING

All Serious Adverse Events (SAEs) that occur following the subject's written consent to participate in the study through 30 days of discontinuation of dosing must be reported to Bristol Meyers Squibb (BMS) Worldwide Safety.

Adverse Events

- An Adverse Event [AE] is defined as any new untoward medical occurrence or worsening of a pre-existing medical condition in a patient or clinical investigation subject administered an investigational (medicinal) product and that does not necessarily have a causal relationship with this treatment. An AE can therefore be any unfavorable and unintended sign (including an abnormal laboratory finding, for example), symptom, or disease temporally associated with the use of investigational product, whether or not considered related to the investigational product.
- The causal relationship to study drug is determined by a physician and should be used to assess all adverse events (AEs). The causal relationship can be one of the following:
 - Related: There is a reasonable causal relationship between study drug administration and the AE.
 - Not Related: There is not a reasonable causal relationship between study drug administration and the AE.
- The term "reasonable causal relationship" means there is evidence to suggest a causal relationship.
- Adverse events can be spontaneously reported or elicited during open-ended questioning, examination, or evaluation of a subject. (In order to prevent reporting bias, subjects should not be questioned regarding the specific occurrence of one or more adverse events).

Serious Adverse Events

A Serious Adverse Event (SAE) is any untoward medical occurrence at any dose that:

- results in death

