Serious Adverse Event Collecting and Reporting

Following the subject's written consent to participate in the study, all SAEs, whether related or not related to study drug, must be collected, including those thought to be associated with protocol-specified procedures. All SAEs must be collected that occur during the screening period and within 30

days of discontinuing dosing. If applicable, SAEs must be collected that relate to any later protocolspecific procedure (such as follow-up skin biopsy).

The investigator should report any SAE occurring after these time periods that is believed to be related to study drug or protocol-specified procedure.

An SAE report should be completed for any event where doubt exists regarding its status of seriousness.

If the investigator believes that an SAE is not related to study drug, but is potentially related to the conditions of the study (such as withdrawal of previous therapy, or a complication of a study procedure), the relationship should be specified in the narrative section of the SAE Report Form.

SAEs, whether related or unrelated to the study drug, and pregnancies must be reported to BMS within 24 hours. SAEs must be recorded on the SAE Report Form; Pregnancies on a Pregnancy Surveillance Form.

SAE Email Address: [contact]

SAE [contact]

If only limited information is initially available, follow-up reports are required. (Note: Follow-up SAE reports should include the same investigator term(s) initially reported.)

If an ongoing SAE changes in its intensity or relationship to study drug or if new information becomes available, a follow-up SAE report should be sent within 24 hours to the BMS (or designee) using the same procedure used for transmitting the initial SAE report.

All SAEs should be followed to resolution or stabilization.

SAE Reconciliation

The investigator will reconcile the clinical database SAE cases transmitted to BMS Global Pharmacovigilance (GPV&E). Frequency of reconciliation will be every three months and once prior to study database lock. BMS GPV&E will e-mail upon request from the investigator, the GPV&E reconciliation report. Requests for reconciliation should be sent to [contact]. The data elements listed on the GPV&E reconciliation report will be used for case identification purposes. If the investigator determines a case was not transmitted to BMS GPV&E, the case will be sent immediately.

Health Authority Reporting (US FDA IND)

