The study does not have funding to pay for any medical complications of study participation. The participants would therefore assume the potential financial risk of unanticipated medical care costs.

9. Benefits

a. Description of the probable benefits for the participant and for society. There may be no benefit to the participant. Potential benefits to society include improved knowledge about prophylaxis with oral anticoagulation medications during bariatric surgery and following surgery when treating a prior bariatric surgical patient with an oral anticoagulation medication for a medical condition such as stroke or atrial fibrillation.

10. Payment and Remuneration

a. Detail compensation for participants including possible total compensation, proposed bonus, and any proposed reductions or penalties for not completing the protocol.

To compensate patients for their time and participation - \$250.00 plus a parking pass will be given per visit completed:

Visit 1: **Pre-op**: 24 hours inpatient/48 hour blood draw outpatient/72 hour blood draw outpatient \$250.00 completed visit

Visit 2: **1 month**: 24 hours inpatient/48 hour blood draw outpatient/72 hour blood draw outpatient \$250.00 completed visit

Visit 3: **6 month**: 24 hours inpatient/48 hour blood draw outpatient/72 hour blood draw outpatient \$250.00 completed visit

Visit 4: **12 month**: 24 hours inpatient/48 hour blood draw outpatient/72 hour blood draw outpatient \$250.00 completed visit

Final Exit Interview by telephone (two weeks following visit #4): Review any adverse events that may have occurred. No compensation at this time.

The total amount of compensation possible is \$1,000.00 plus parking.

11. Costs

a. Detail costs of study procedure(s) or drug (s) or substance(s) to participants and identify who will pay for them.

No costs to the participants.

Table 3. Timeline for Study

	Year 1				Year 2			
TASK	July 2016	Oct. 2016	Jan. 2017	April 2017	July 2017	Oct. 2016	Jan. 2018	April 2018
Submission of Grant to BMS								

and Organization of Study				
Materials and supplies				
Database creation/testing				
JHU IRB approval				
Recruitment and enrollment				
Data collection				
Enter and clean data				
Data quality review				
Analyze data				
Abstract submissions				
Manuscript preparation				
Preparation of other grants				

References

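### The last planned participant contact comes about two weeks before the 30-day SAE window closes, so no scheduled contact supports collection in the final 13 to 16 days

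*Combined protocol and SAP*

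**What the plan says.** Three parts of the protocol bear on this.

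**Schedule.** In Section 4a, Table 1 gives the fourth and last dosing visit as "12 Months (12 to 14 months) Post-bariatric surgery * (study participant receives one 5 mg dose of apixaban". The row after it is the exit contact, "Final Exit Interview Visit (two weeks following final visit", with the task "Review any adverse events that may have occurred throughout entire study". Section 10 lists the same contact as "Final Exit Interview by telephone (two weeks following visit #4". No later visit, call or diary appears anywhere.

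**SAE window.** Section 8, under Adverse Event Reporting, says that SAEs from consent "through 30 days of discontinuation of dosing must be reported to Bristol Meyers Squibb (BMS) Worldwide Safety". The later subsection on collecting and reporting SAEs makes this a collection duty: "All SAEs must be collected that occur during the screening period and within 30", the sentence then continuing to days from the end of dosing. That duty does not depend on causality. Section 8 also says that pregnancies must be handled as SAEs.

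**Early discontinuation.** Section 4g promises an exit interview with a final assessment but gives no date for it.

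**The concern.** The call meant to review adverse events over the whole study takes place before the period in which SAEs must be collected has ended. After it, nobody at the site is scheduled to ask the participant anything. What is at stake is the completeness of SAE ascertainment after the fourth dose.

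Pregnancy is a concrete example. Section 8 requires a negative test shortly before dosing and names a late period as a warning sign. It is my inference, not a statement in the protocol, that a pregnancy beginning around the last dose could go unrecognised at a two-week call.

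Participants who stop early are exposed in a different way: their exit interview has no stated timing, so 30-day coverage after their last dose is not assured. Section 7c allows for five losses in each group of 15, or up to 10 of 30 participants, though the plan does not say how many of those would have an exit interview.

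**Working it through.** The plan states no figure for coverage of the window, so there is none to reproduce. The check is calendar arithmetic.

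**Inputs**
- Last dose: the single dose at visit 4 (Table 1). Call this day 0.
- Length of the dosing visit: 24 hours as an inpatient, then return draws. Section 4a says "The participant will then be asked to return back to the CRU for one blood draw at 48 hours and one blood draw at 72" (both times counted from dosing, each with a window of ±4 hours). The visit therefore runs from day 0 to about day 3.
- Exit contact: 14 days after visit 4 (Table 1, Section 10).
- SAE window: 30 days from the end of dosing (Section 8).

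**Formulas**
- Contact day = anchor day + 14
- Days without planned contact = 30 − contact day
- Share = days without planned contact / 30

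The protocol does not say which point of visit 4 starts the two weeks, so each plausible anchor is shown.

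| Anchor | Contact day | Days without contact | Share of 30 |
|---|---|---|---|
| Dose (day 0) | 14 | 16 | 53% |
| 24-hour discharge (day 1) | 15 | 15 | 50% |
| 72-hour draw (day 3) | 17 | 13 | 43% |

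The ±4 hours on the 72-hour draw moves the last row only to between 12.8 and 13.2 days.

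**Are the earlier windows affected?** Visit 1 is at least 3 weeks before surgery and visit 2 at least 4 weeks after it, so they are at least 7 weeks (49 days) apart. Visit 2 is at most 6 weeks after surgery and visit 3 at least 6 months after it. Visit 3 is at most 8 months after surgery and visit 4 at least 12 months after it, a gap of at least 4 months. In every case the next visit falls beyond day 30 and can pick up SAEs in retrospect. Only the window after visit 4 has no later contact.

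**Does anything else fill the gap?** Section 8b promises close observation around study visits but attaches no dates beyond the 24-, 48- and 72-hour checks. The three-monthly SAE reconciliation in Section 8 compares the clinical database with the company's safety database. It involves no participant contact and cannot find an event that was never recorded.

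**After the change.** With a contact on day 30 or later, days without coverage fall to 0 of 30. That moves the call at least 30 − 14 = 16 days later if the two weeks run from the dose, or 30 − 17 = 13 days later if they run from the 72-hour draw.

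**The case against.** The strongest reply is that nothing is contradictory here. Section 8 places a duty on the investigator and Table 1 schedules a call. No sentence says that SAE collection ends with the call, and Section 8 goes further by asking for related SAEs after the window and for follow-up to resolution or stabilization. That stands: a reader might infer two conflicting rules, but both can be met. The defect is a missing contact, not a missing requirement.

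A reader might also infer that late events are recorded only if a participant telephones unprompted. The documents do not support that. Participants are patients of the same bariatric center, so routine care could bring an event to light, and Section 8b promises some monitoring, though undated.

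A third inference would be that a reported 30-day safety result is undermined, or that late bleeding or liver events will be missed. Section 7 plans no 30-day safety summary or SAE rate, and Section 6c says that the study is not meant to assess clinical outcomes. Nothing in the documents places a drug-related risk in the second half of the 30 days after one dose.

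The denominator is also open to challenge. Over all four 30-day post-dose windows, the gap is 13/120 to 16/120, or 11% to 13%. That is fair as a description of the whole study, but the duty applies to each window, and the last is the one with no later contact.

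Finally, the point that one dose clears quickly does not answer the concern, because the window covers SAEs regardless of cause.

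**Conclusion.** The point holds as a gap in the schedule. For participants who complete visit 4, the last 13 to 16 days of the final 30-day SAE window have no planned contact; about half is right under every reading of the two weeks. For early stoppers the size cannot be computed, because Section 4g gives no timing.

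This rests on two assumptions: that the end of dosing means the visit 4 dose for completers, and that two weeks means 14 days.

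The consequence is limited to how completely SAEs are ascertained after the last dose. Sample size, power and the pharmacokinetic and pharmacodynamic comparisons are untouched. It is worth correcting because the remedy is small, not because a planned result is at risk.

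**What to change.** Reconcile Table 1, Section 10 and Section 4g with the SAE window in Section 8, in one of two ways.

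1. **Move the exit call** to the day the 30-day window closes or later. No contact is added, and each participant is followed for about two weeks longer. The drawback is recall: after the 72-hour draw, the next contact would be about 27 days later (day 3 to day 30), so events in the first two weeks would be learned of later than they are now.
2. **Keep the two-week call and add a brief one** at the close of the window. This preserves early ascertainment and costs one more telephone call per participant.

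Either way, Section 4g should tie the early-discontinuation interview, or an added call, to the close of the window after that participant's last dose. The protocol should also say which point of visit 4 starts any interval counted from it.

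While those lines are open, settle how the exit contact is described: Table 1 calls it a visit, Section 10 a telephone call, and Section 4b counts only four visits. The edits are a few lines in three places, with no new sample, procedure or clinic attendance.

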Cover Page

APB Study: Apixaban Pharmacokinetics in Bariatric Patients

Objective: A study to determine the pharmacokinetics and pharmacodynamics of apixaban in obese patients who undergo bariatric surgery.

NCT02406885

IRB: IRB00035495 The Johns Hopkins University School of Medicine Note: Principal Investigator change/update – [name]

JHM IRB - eForm A – Protocol

- Use the section headings to write the JHM IRB eForm A, inserting the appropriate material in each. If a section is not applicable, leave heading in and insert N/A.
- When submitting JHM IRB eForm A (new or revised), enter the date submitted to the field at the top of JHM IRB eForm A.

APB Study: Apixaban Pharmacokinetics in Bariatric Patients

A study to determine the pharmacokinetics and pharmacodynamics of apixaban in obese patients who undergo bariatric surgery.

1. Abstract

a. Provide no more than a one page research abstract briefly stating the problem, the research hypothesis, and the importance of the research.

Obesity is now the leading health problem of the 21st century. Weight reduction by conservative methods including diet and exercise has had poor success rates. There has been a substantial increase in the use of bariatric surgery to provide sustained weight loss and thus a reduction in the medical comorbidities that are associated with obesity. However, because these procedures may alter the anatomical and physiological aspects of the gastrointestinal system, there is a possibility of altered pharmacokinetics to medications particularly when taken orally. Furthermore, patients typically lose anywhere from 50 to 75% of their estimated excess body mass approximately one to two years following surgery. This successful therapeutic outcome of the surgery may be causing long term changes in the pharmacokinetics that are independent of any direct anatomical or physiologic changes induced by the procedure.

Physicians and surgeons are very interested in oral anticoagulants for this special patient population. To date, there is no approved dosing for the obese patient (especially when considering surgical

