Hypothesis 2b: Patients who have recently undergone VSG surgery (1 month post-op) will have a decrease in both the Cmax and AUC, relative to pre-op values, when given a single dose of 5 mg of apixaban. The magnitude of the decrease in Cmax and AUC will be less than that seen in RYGB patients.

Rationale: Anatomic alteration of the GI tract will immediately reduce absorption in all postoperative bariatric patients. In RYGB patients, the attenuated small bowel and altered bile acid composition will lead to decreased absorption of the drug, whereas in sleeve gastrectomy patients prolonged gastric emptying may affect pharmacokinetics. These findings will be important when considering the use of apixaban as an oral anticoagulation option for perioperative VTE prophylaxis in the bariatric population, both in the acute hospital setting and after discharge in patients requiring extended VTE prophylaxis or treatment.

Hypothesis 2c: After undergoing bariatric surgery, patients at 6, and 12 months post-op will have an increase in Cmax and AUC, relative to pre-op values, when given a single dose of 5 mg of apixaban.

Hypothesis 2d: After undergoing RYGB, patients at 6, and 12 months post-op will have a greater increase in both Cmax and AUC, relative to pre-op values, than VSG patients relative to pre-op values when given a single dose of 5 mg of apixaban.

Rationale: Patients who are 6 to 12 months post-bariatric surgery generally have a 30-50% decrease in excess body weight. This decrease in body weight reduces volume of distribution of drug, potentially affecting Cmax. Results of the published Phase 1 apixaban study found that exposure to a dose of apixaban was inversely related to body weight. Therefore, we should expect higher plasma levels of apixaban in patients who are 6 to 18 months post-bariatric surgery when compared to pre-op values.

Findings of the Phase I study (3,4)

An open-label, parallel-group, non-randomized, single-dose study in healthy male and female subjects was conducted to assess the effects of body weight on the pharmacokinetics of a single 10 mg dose of apixaban. Following screening, patients were enrolled in one of three groups: low body weight (≤50kg, N=18), normal body weight (65-85kg, N=18) or high body weight (≥120kg, N=19).

Compared to normal body weight:

- There was a 27% increase in Cmax and 20% increase in AUC in patients with low body weight

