c. Blinding, including justification for blinding or not blinding the trial, if applicable. N/A

d. Justification of why participants will not receive routine care or will have current therapy stopped.

There will be no effect on routine clinical care.

e. Justification for inclusion of a placebo or non-treatment group. N/A

f. Definition of treatment failure or participant removal criteria The participants will be removed from the study if they develop a clinically significant illness or a major bleeding complication attributed to apixaban (as opposed to minor issues, which need

not remove the participant from the study).

g. Description of what happens to participants receiving therapy when study ends or if a participant's participation in the study ends prematurely.

If the subject discontinues early, will we conduct an exit interview with final assessment.

5. Inclusion/Exclusion Criteria Inclusion Criteria:

- Men or women, 18 to 65 years old with a BMI of 35 kg/m² or greater who will be undergoing bariatric surgery (VSG and RYGB).
- Signed written informed consent
- Women of childbearing potential (WOCBP) must have a negative serum or urine pregnancy test (minimum sensitivity 25 IU/L or equivalent units of HCG) within 24 hours prior to the start of study drug.
- Women must not be breastfeeding

Exclusion Criteria:

- History of documented clotting/coagulation disorder.
- History of cancer (within the last year)
- Any diagnosis requiring anti-coagulation
- History of hypersensitivity reaction to apixaban
- Active clinically significant bleeding
- GFR < 30
- Participant who has moderate-severe liver disease (Child-Pugh B or C)

- Participants currently receiving any type of anticoagulation or blood thinning medications, including heparin, low molecular weight heparins, Plavix, aspirin, NSAIDS
- Participant who is taking any of the excluded medications (see Table 2 above)

6. Drugs/ Substances/ Devices

a. The rationale for choosing the drug and dose or for choosing the device to be used.

Drug procurement, handling, accountability and destruction will be carried out by the Johns Hopkins Bayview Research Pharmacy. Administration of the drug will be completed by nursing staff in the CRU. These nurses will be trained and familiar with the protocol.

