To determine the durability or change in pharmacokinetics and pharmacodynamics of apixaban in patients with a body mass index (BMI) of 35 kg/m² or greater following one of two bariatric surgical procedures (pre-operative versus post-operative vertical sleeve gastrectomy or Roux-en-Y gastric bypass patients).

b. Secondary outcome variables.

1. To compare/contrast the pharmacokinetics and pharmacodynamics of apixaban in bariatric surgical patients who have undergone RYGB vs. VSG.

2. To determine how the pharmacokinetics of the drug may differ when there is significant post-operative surgical weight loss (>40% estimated excess body weight) 12 months following surgery versus those patients who have suboptimal weight loss following bariatric surgery (< 40% of estimated excess body weight).

c. Statistical plan including sample size justification and interim data analysis.

We propose to study 15 subjects in each arm (RYGB vs. VSG) and use them as their own controls. We have accounted for loss to follow-up (even with a 36% (5 in each group) drop-out rate, we would have enough subjects (10 per group) to demonstrate a 36 % change in AUC with an alpha error of 0.05 and a beta error of 0.2 (Power of 80%). If there is no loss to follow-up and all patients remain in the study, this will allow us to demonstrate a 29% change in AUC with an alpha error of 0.05 and a beta error of 0.2.

These calculations were calculated based on the following data from Upreti et al.: Ratio of geometric mean point estimated for high body weight (>120 kg) vs. normal body weight for C_{max} = 0.692 (0.586, 0.818) and AUC (INF) = 0.77 (0.652, 0.912).

Routine pharmacokinetic data will be determined, including C_{max}, T_{max} and AUC for each subject at each dosing time, and compared within subjects and between subjects and between groups. Factor Xa activity will be compared to apixaban concentration at each time point.

d. Early stopping rules.

While we do not expect to have any serious adverse events related to the administration of a single dose of 5 mg of apixaban as required in this study, we will interrupt the study and report to the IRB if 10% or more of our first 12 subjects suffer a serious adverse event "definitely

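### Secondary outcome 2 splits patients at 40% of excess weight lost, although the PK rationale rests on body weight; the split mixes weight loss with starting BMI and discards much of the information on weight change

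*Combined protocol and SAP*

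**What the plan says.** Section 7b item 2 sets patients with "significant post-operative surgical weight loss (>40% estimated excess body weight) 12 months following surgery versus those patients who have suboptimal weight loss" against those with "suboptimal weight loss following bariatric surgery (< 40% of estimated excess body weight". Neither class includes exactly 40%, and the weight from which the excess is measured is not given. It is also not said whether the comparison concerns 12-month values or change from before surgery. Section 7c adds only that PK values are compared within subjects, between subjects and between groups, and that patients act as their own controls. No analysis by kilograms lost, percent of body weight lost or current weight is planned, and none adjusts for starting BMI.

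Section 5 admits patients "with a BMI of 35 kg/m² or greater who will be undergoing bariatric surgery", with no upper limit.

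The reason to expect a weight effect is in section 2, in the rationale after Hypotheses 2c and 2d: "Results of the published Phase 1 apixaban study found that exposure to a dose of apixaban was inversely related to body weight", and "This decrease in body weight reduces volume of distribution of drug, potentially affecting Cmax". The study cited there grouped people by kilograms (50 or less, 65-85, 120 or more).

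On the loss to be expected, the same rationale says that patients at 6 to 12 months "generally have a 30-50% decrease in excess body weight", while the Abstract says that "patients typically lose anywhere from 50 to 75% of their estimated excess body mass approximately one to two years following surgery". The footnote to Table 1 treats a loss of at least 30% to 50% of excess weight by 12 months as the ideal.

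**The concern.** The outcome asks how weight loss changes PK, but the grouping variable is a measure of surgical success rather than of weight change. Its denominator is the excess over a reference weight, and that excess grows quickly with starting BMI. The same 40% therefore means a small loss of body weight in a lighter patient and a large one in a heavier patient. A heavy patient can lose a greater share of body weight and still fall in the lower class.

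Two things are at stake. First, a real relation between weight loss and exposure would be diluted, and a null result could be read as showing that weight loss does not matter. Second, any difference that is found would be confounded with starting BMI, because the lower class tends to start heavier.

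**Working it through.** The plan gives no figure for this outcome, so there is none to reproduce. The detectable AUC changes in section 7c (36% with 10 per group, 29% with 15) serve below only as a yardstick.

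**Inputs from the documents.** Cut at 40% (7b item 2); entry BMI 35 or more (section 5); AUC ratio 0.77, high against normal weight (7c); 15 per arm, 10 after dropout (7c).

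**Assumptions.** Reference BMI 22 to 25; height 1.65 m; mean weights in the cited study of 75 kg (normal) and 120 to 150 kg (high).

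**1. What the cut means in body weight.** Fraction of excess lost = (W0 − W1)/(W0 − Wref). It follows that

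- fraction of body weight lost = fraction of excess lost × (BMI0 − BMIref)/BMI0
- kg lost = fraction of excess lost × (BMI0 − BMIref) × height²

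| Starting BMI | Reference BMI 25 | Reference BMI 22 |
|---|---|---|
| 35 | 0.40 × 10/35 = 11.4% | 0.40 × 13/35 = 14.9% |
| 45 | 0.40 × 20/45 = 17.8% | 0.40 × 23/45 = 20.4% |
| 60 | 0.40 × 35/60 = 23.3% | 0.40 × 38/60 = 25.3% |

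**2. Two patients, 1.65 m (height² = 2.7225), reference BMI 25.**

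- Patient A: BMI 60, 35% of excess lost, lower class. Loss 0.35 × 35 × 2.7225 = 33.4 kg, or 0.35 × 35/60 = 20.4% of body weight.
- Patient B: BMI 36, 45% of excess lost, upper class. Loss 0.45 × 11 × 2.7225 = 13.5 kg, or 0.45 × 11/36 = 13.75%.

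With reference BMI 22 the order is the same: 36.2 kg (22.2%) against 17.2 kg (17.5%).

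**3. What this implies for AUC.** Fit a power law to the ratio 0.77: k = ln(0.77)/ln(120/75) = −0.556, or ln(0.77)/ln(150/75) = −0.377. Patient A: 0.796^k gives a rise of 9.0% to 13.5%. Patient B: 0.8625^k gives 5.7% to 8.6%. The lower-class patient has the larger predicted change, by about 3 to 5 percentage points.

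**4. The unstated reference weight.** A patient of 120 kg and 1.65 m loses 22 kg. With reference BMI 25 (68.06 kg): 22/51.94 = 42.4%, upper class. With reference BMI 22 (59.90 kg): 22/60.10 = 36.6%, lower class.

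**5. Group level, by simulation.** Assumed: 20 to 30 patients, right-skewed starting BMI with median about 44 to 45, percent of body weight lost independent of BMI with mean 15-30% and SD 6 or 9 points, reference BMI 22 or 25.

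- The split captured about 24-60% of the variance in ln(weight) change, so about 40-76% was lost.
- The continuous regression had about 1.4 to 3 times the power of the split. This also depends on the assumed slope and residual spread, which the documents do not give.
- The lower class typically started 4 to 6 BMI units heavier. With 20 completers it held from about 16 patients down to about 2.
- Group means essentially never reversed on percent of weight. On kg they mostly reversed in under 3% of trials, rising to about 11% or somewhat more where the smaller class was nearly empty.

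**The case against.** Excess weight is the metric that the protocol uses throughout, and surgeons know it. Item 2 can be read as a question about successful against suboptimal surgical responders. No numbered hypothesis uses the 40% split, and the primary comparison before and after surgery does not touch it. This stands, and it limits the weight of the point. It does not make the split a good exposure variable for a question about weight and PK.

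The cited study compared people at different weights, not people losing weight. If item 2 concerns 12-month exposure levels, the class order agrees with attained weight in the example: patient A ends at 130.0 kg and patient B at 84.5 kg, so B would be expected to have the higher exposure. That is correct, and the text leaves this reading open. But such a contrast would largely reflect who was heavier from the start, which is the confounding at issue. The own-controls wording in 7c points towards change.

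The 3 to 5 point gap between the two patients is far below the 29% to 36% that 7c calls detectable. This also stands: no analysis of 20 to 30 patients will measure the weight effect precisely, and the power law carries between-person data from healthy volunteers over to operated patients. It is a reason not to discard information.

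A cut in the middle of the expected 30-50% range gives balanced classes. That is fair for that range, but not for the Abstract's 50-75%.

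A slope on weight change alone would be confounded by procedure, because section 2 (after the Phase I findings) says that RYGB combines greater weight loss with reduced absorption. This is accepted, and the fix includes procedure.

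**Conclusion.** The concern holds at the level of the measure. The grouping in 7b item 2 does not follow the weight change on which the protocol's rationale rests. One cut stands for about 11% to 23% of body weight between BMI 35 and BMI 60 (reference BMI 25 assumed; 15% to 25% with reference 22). Individuals can be misranked, and roughly 40-75% of the information on weight change is lost under the distributions assumed above.

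A reader might infer that the lower class as a whole would show the larger weight loss, so that the result would run backwards. The documents do not support this. It takes selected patients, and under ordinary distributions group means hardly ever reverse on the percent scale and seldom on kg. The expected harm is dilution and confounding with starting BMI.

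A reader might also infer that the lower class will be nearly empty. That follows only if the Abstract's 50-75% applies at visit 4. Section 2 gives 30-50% at 6 to 12 months, and the documents do not settle which range applies. On that range, and on the Table 1 footnote, a patient at 35% would be within the ideal range and also in the lower class.

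The primary outcome is unaffected. The point is a cheap improvement.

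**What to change.** Restate the main analysis of 7b item 2 as a regression of within-patient change in ln(AUC) and in ln(Cmax), visit 1 to visit 4, on change in ln(body weight) over the same visits, with procedure (RYGB or VSG) as a covariate. Report the slopes with confidence intervals. State that weight is recorded at both visits.

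Keep the 40% split as a descriptive table, with the reference weight defined and exactly 40% assigned to one side.

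The cost is wording in 7b and one regression model per PK measure. No new data are needed, since the present outcome already requires the weights before surgery and at 12 months. A slope is less familiar to surgeons than a split into success and failure, which the table preserves. The procedure term costs one degree of freedom and, because procedure and weight loss are expected to go together, will widen the interval for the slope.
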